We hypothesize that the iLet BP will be non-inferior to the iPhone-based BP in dose administration and blood glucose control while subsequently improving user satisfaction with the device. We also hypothesize that Xeris glucagon in the iLet BP will be non-inferior to Lilly glucagon in the iLet BP in both infusion site reactions and occlusions.

In the Infusion Set Sub-Study, we hypothesize that the iLet infusion set will be non-inferior to the Contact Detach infusion set in plasma insulin levels, blood glucose control, and user experience.

The specific aims of this study are:

Aim 1. To conduct an outpatient study testing the safety and efficacy of the iLet BP versus our iPhone-based BP in up to 10 adult (≥ 18 years of age) subjects with type 1 diabetes in the fasted state, after a meal, and during and after exercise.

The study for this Aim will consist of two 8-hour study arms in random order: one with the iPhone-based BP and one with the iLet BP. Subjects will arrive fasting and remain fasted until the lunch meal. They will exercise on a stationary bike bpm for approximately 30 minutes with a heart rate from 120–140, starting at least 2 hours after lunch. The primary outcome will be the average percent dose amounts of both insulin and glucagon calculated by the control algorithm that are successfully delivered by the pump. Important secondary outcomes will include other metrics of device function (plasma insulin and glucagon levels will be measured every 30 minutes throughout the experiment) and measures of glycemic regulation, including mean CGM glucose and hypoglycemia exposure (% time <60 mg/dl).

Aim 2. To conduct an outpatient study testing the safety and efficacy of the iLet BP with Lilly glucagon versus Xeris glucagon in up to 10 adult (≥ 18 years of age) subjects with type 1 diabetes

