- User satisfaction

VI. b. 3. Secondary endpoint analyses – Bionic Pancreas Function:

This will be generated from the bionic pancreas data during each visit:

- Average percent insulin dose amounts calculated by the bionic pancreas control algorithm that are successfully delivered by the pump.

- Average percent glucagon dose amounts calculated by the bionic pancreas control algorithm that are successfully delivered by the pump.
- Average percent dose amounts successfully issued to the pump by the bionic pancreas control algorithm that are successfully delivered by the pump (calculated doses are not issued unless the pump is accessible and its delivery channel is available).
 - Average percent insulin dose amounts successfully issued to the pump by the bionic pancreas control algorithm that are successfully delivered by the pump.
 - Average percent glucagon dose amounts successfully issued to the pump by the bionic pancreas control algorithm that are successfully delivered by the pump.
- Average percent dose amounts calculated by the bionic pancreas control algorithm that are successfully issued to the pump by the bionic pancreas (calculated doses are not issued unless the pump is accessible and its delivery channel is available).
 - Average percent insulin dose amounts calculated by the bionic pancreas control algorithm that are successfully issued by the bionic pancreas.
 - Average percent glucagon dose amounts calculated by the bionic pancreas control algorithm that are successfully issued by the bionic pancreas.
- Average percent of 5 minute steps during which the bionic pancreas is functioning nominally in all respects based on real-time CGM data (new CGM glucose reading captured, dose calculated, dose issued to pumps,
- Average percent of 5 minute steps during which the bionic pancreas is functioning nominally with or without a new CGM glucose reading captured (dose calculated, dose issued to pumps). If a CGM signal is not available, the dose calculated may be based on weight-based or historical basal rates.
- CGM reliability index, calculated as percent of possible values actually recorded by CGM.
- CGM MARD versus time-stamped BG values from YSI.
- List of technical faults associated with the bionic pancreas including cause and resolution.

VI. b. 4. Secondary endpoint analyses – Glycemic:

- All of following metrics will be generated from the DexCom G4 Platinum CGM data during each bionic pancreas visit.
 - Mean CGM glucose.

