 - Fraction of time spent within each of the following glucose ranges:
 - < 50 mg/dl.
 - < 60 mg/dl.
 - < 70 mg/dl.
 - 70-120 mg/dl.
 - 70-180 mg/dl.
 - >180 mg/dl.
 - >250 mg/dl.
 - Percentage of subjects with mean CGM glucose < 154 mg/dl (estimated average glucose corresponding to an A1c of 7%).
- Number of severe hypoglycemic events (subject unable to self-treat, requiring the assistance of another person).

During Exercise

- Number of subjects discordant for reaching a BG < 60 mg/dl (measured with YSI) for > 2 consecutive plasma glucose measurements
- Area between the glucose curve and 60 mg/dl calculated from BG measurements
- Area between the glucose curve and 60 mg/dl calculated from CGM data
- Time from start of exercise to first BG measurement < 60 mg/dl
- Time from start of exercise to first CGM measurement < 60 mg/dl

VI. b. 5. Secondary endpoint analyses – Non-glycemic

- Glucagon total delivery per kg of body mass.
- Insulin total delivery per kg of body mass.
- Number of episodes of symptomatic hypoglycemia.
- Number of carbohydrate interventions for hypoglycemia.
- Total grams of carbohydrate taken for hypoglycemia.

- Difference in mean nausea from VAS during the study (mean of measurements every 2 hour and at study end) vs. baseline at study start.
- Difference in Infusion site pain from VAS during the study (mean of measurements every 2 hour and at study end) vs. baseline at study start. Note that in the iLet infusion set the infusion catheters are 1 cm apart, so it may not be possible to differentiate whether a sensation is coming from the insulin or glucagon infusion catheter. Subjects will be asked to use their best judgment and to provide scores for both catheters.
- Difference in local erythema and edema according to the Draize scale (mean of measurements every 2 hour and at study end) vs. baseline at study start. Note that in the iLet infusion set the infusion catheters are 1 cm apart, so it may not be possible to differentiate whether a skin reaction is coming from the insulin or glucagon infusion catheter. Subjects will be asked to use their best judgment and to provide scores for both catheters.
- Number of unscheduled infusion set replacements.
- Number of unscheduled CGM sensor changes.

During Exercise

- Grams of oral carbohydrates given to the subject to treat hypoglycemia
- Total glucagon dosing by bi-hormonal bionic pancreas from the start of exercise until the end of the visit

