The main criteria for the success of the study will be that we observe a significant improvement in the primary outcome measure (and the related secondary reliability measures) in the iLet vs. the iPhone-based BPs, and no significant difference in the glycemic control measures. It is possible that improved reliability may actually improve glycemic control measures, but the sample size may not be sufficient to detect any such difference. A secondary criterion for success of the study will be that we observe no statistical difference in safety-related outcomes (occlusions, infusion site reactions or pain, nausea) between Xeris and Lilly glucagon.

The main criteria for the success of the infusion set sub-study will be that we observe no significant difference in the performance of the iLet infusion set when compared with the Contact Detach. Achieving a non-inferior result would allow us to move forward in future testing of the iLet infusion set with the iLet bionic pancreas in outpatient trials.

VII. Risks and Discomforts

Subjects may experience mild discomfort associated with the insertion of the infusion sets and sensor into the SC tissues. The risk of discomfort due to insertion of infusion sets and sensors is expected to be greater than in their lives outside the trial because more infusion sets will be inserted and a CGM sensor will be inserted, which may not be used in usual care.

There is a potential risk of hypoglycemia, since exogenous insulin will be administered. Due to frequent monitoring of glucose and direct supervision by an RN or MD at all times, the risk of a hypoglycemic episodes leading to significant harm to volunteers is expected to be substantially lower than their risk during their usual therapy.

There is a risk of hyperglycemia. This risk is expected to be less than the risk during the subjects' lives outside of the trial based on data from earlier trials.

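### The glycemic limb of the main success criterion (VI.d) has no direction, named measure or margin, so read literally a significant glycemic improvement with the iLet fails it

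*Combined protocol and SAP*

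**What the plan says.** Section VI.d (Criteria for Success of the Study) joins two conditions for the iLet versus the iPhone-based system. The reliability condition has a direction: "we observe a significant improvement in the primary outcome measure (and the related secondary reliability measures"). The glycemic condition does not, and the sentence after it foresees an improvement: "and no significant difference in the glycemic control measures. It is possible that improved reliability may actually improve glycemic control measures". That sentence goes on to say only that the sample may be too small to detect such a difference. It does not say how a detected improvement would be scored.

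Two other sections state the aim differently.

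- Section II: "We hypothesize that the iLet BP will be non-inferior to the iPhone-based BP in dose administration and blood glucose control". This is one-directional. No margin is given.
- Section I.d describes the study as establishing equivalence between the two systems, primarily in functionality, user safety, accuracy and component reliability. It leaves comprehensive efficacy to later, larger studies.

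VI.d does not list the glycemic measures it means. Aim 1 in section II singles out, among its important secondary outcomes, "measures of glycemic regulation, including mean CGM glucose and hypoglycemia exposure (% time <60 mg/dl"). Section VI.b.4 is much longer. It opens with "All of following metrics will be generated from the DexCom G4 Platinum CGM data during each bionic pancreas visit" and lists mean CGM glucose, seven ranges under "Fraction of time spent within each of the following glucose ranges", and the percentage of subjects with a mean below 154 mg/dl, which makes nine CGM metrics. With the severe hypoglycemia count and five exercise items the total is 15. The analysis text after VI.b.5 prescribes a paired t-test or Wilcoxon signed rank test and gives no multiplicity rule.

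**The concern.** A success rule should become easier to meet as the device gets better. This limb becomes harder to meet, because the more the iLet improves glucose control, the more likely a significant difference is. The plan foresees that case and answers only that the sample may be too small to detect it. If a benefit were detected, the sponsor would have to report failure on the written rule or grant an exemption after seeing the data.

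The limb is also weak in the other direction. With no margin, it treats a non-significant result from about 10 subjects as evidence that control is unchanged.

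**Working it through.** **The plan's own figure.** VI.c gives 25, 10 and 8 subjects for availability of 98%, 99.2% and 99.6% against 96%, with SD 2.5, two-sided 5% alpha and 80% power. Using n = 2(1.960 + 0.842)² × 2.5² / Δ²:

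- Δ = 2.0: 24.5, rounded up to 25
- Δ = 3.2: 9.6, rounded up to 10
- Δ = 3.6: 7.6, rounded up to 8

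The figures reproduce and are not in dispute. They concern the primary outcome only; no figure is given for the glycemic limb.

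**Inputs for the glycemic limb.** n = 10 pairs is the upper figure for completers in IV.a. The two-sided 5% level is taken from VI.c, which states it only for the primary outcome. The effect d (true mean paired difference divided by the SD of the differences) is assumed, because the documents give no paired SD for any glycemic measure.

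**One measure.** The paired t statistic has 9 degrees of freedom, critical value 2.262 and noncentrality d√10. The observed mean difference is therefore significant once it exceeds 2.262/√10 = 0.72 SD of the differences. The chance of failing the limb is P(|t| > 2.262).

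| True benefit d | Literal rule fails | Fails if only significant worsening counts (same cut-off) |
|---|---|---|
| 0 | 5.0% | 2.5% |
| 0.5 | 29.3% | 0.03% |
| 0.8 | 61.6% | <0.01% |
| 1.0 | 80.3% | <0.01% |

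By symmetry, a device truly worse by d = 0.5 trips the literal rule 29.3% of the time and passes about 71% of the time. A one-sided 5% harm test (critical value 1.833) has about 43% power at d = 0.5, so such a device would still pass about 57% of the time. Changing the direction alone does not establish absence of harm.

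**Nine CGM metrics, any one of which trips the rule.** If independent, 1 − 0.95⁹ = 37%. The other rows come from 20,000 simulated trials per setting, with equal correlation between metrics and every metric treated as a continuous paired difference. That is an approximation for the below-154 item.

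| Correlation | No glycemic difference | d = 0.5 on every metric |
|---|---|---|
| 0 | 37% | 96% |
| 0.5 | 29% | 76% |
| 0.8 | 18% | 58% |
| 0.95 | 11% | 42% |

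These metrics come from the same CGM trace, so independence is an upper bound rather than a likely value.

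**What cannot be computed.** A non-inferiority sample size needs a margin and a paired SD. The documents give neither.

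**The case against.** The strongest reply is that the two-sided wording is deliberate. Section I.d speaks of equivalence, V.c.2 says both systems run the same algorithms, and V.b expects the same glucagon exposure on both. An unexpected glycemic difference in either direction would then be informative. That stands as a reason to look at both directions. It does not support scoring a benefit as failure, and a non-significant difference does not establish equivalence. It also leaves I.d, II and VI.d with three different objectives.

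A second reply is that the sponsor meant no worse. That is likely, but VI.d does not say it.

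A third is that the effect will be small. This has force. In the I.c table, the whole bionic pancreas lowered mean glucose against control by 16 to 31 mg/dl (158 − 142 and 168 − 137), so shifts of 12 or 20 mg/dl from new hardware would be large. A simulation of 800 trials per case used assumed CGM inputs: baseline 140 mg/dl, log-scale SD 0.30, 60-minute correlation time, between-subject and between-visit SD 0.12. At least one of the nine metrics was significant in 11% of trials with no effect, and in 15% and 17% at reductions of 3 and 5 mg/dl. On Aim 1's two measures alone the figures were 4% and about 6%. The conflict is then uncommon, but it remains.

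A reader might also infer three things that the documents do not support:

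- That every VI.b.4 measure is covered and any one suffices. VI.d uses an unlisted plural, so this is only one reading.
- That an identical device is failed by chance through this limb. Such a device would almost always fail the reliability limb first. The relevant case is a more reliable iLet with unchanged glycemia.
- That improvement is what the sponsor expects. VI.d calls it only possible.

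**Conclusion.** The point holds as a defect of wording in the main success criterion. The literal rule penalizes a detected improvement, disagrees with the one-directional hypothesis in II, names no measure and has no margin. That the chance of failure rises with benefit does not depend on the assumptions. Its size does: 5%, 29% and 80% for one measure at d = 0, 0.5 and 1.0, and 11% to 37% for nine metrics under no glycemic difference on the any-measure reading.

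This should be fixed, but it is not critical. A reader might infer that progress of the study hangs on the rule. The documents attach no stated decision to VI.d, and the step to Aim 2 depends on the iLet performing as expected in Aim 1. The primary endpoint, sample size and data collection are unaffected.

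**What to change.** Revise VI.d as follows.

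1. Make the glycemic limb one-directional: only worsening counts against the iLet. State that an improvement does not count as failure.
2. Judge it on the two measures Aim 1 already names, mean CGM glucose and percentage of time below 60 mg/dl. Report the other VI.b.4 metrics descriptively.
3. Report each paired difference with its confidence interval. Claim non-inferiority only against a margin that the sponsor justifies and fixes before analysis. Without a margin, do not read non-significance as evidence of no harm.
4. Reword the Xeris–Lilly safety sentence in VI.d in the same way, so that only worse outcomes with Xeris count against it, with intervals.
5. Align I.d, II and VI.d on one stated objective for glycemic control.

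The cost is a few sentences and, if non-inferiority is to be claimed, the work of justifying a margin. No new data, visits or subjects are needed. The downside is that intervals from 10 subjects will be wide, so the glycemic conclusion may be more cautious than the present wording allows.

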The study also involves subcutaneous administration of *Xeris glucagon*. Xeris glucagon has the same active pharmaceutical ingredient as Lilly glucagon, but is dissolved in a different vehicle at a higher concentration. Xeris glucagon is dissolved in a non-aqueous solvent that is composed primarily of dimethyl sulfoxide (DMSO) at a concentration of 5 mg/ml, while Lilly glucagon is dissolved in an aqueous vehicle at a concentration of 1 mg/ml. DMSO is listed by the FDA as an inert ingredient and is a component of several approved drug formulations. Xeris glucagon is stable at room temperature for two years (see the Investigator Brochure in Appendix A). The age of the Xeris glucagon at the time of administration will depend on when the experiments are done, but we will complete all of them within the already determined window of stability.

Xeris has performed pre-clinical toxicology study up to 28 days in length in rats, and found the No-observed-adverse-effect-level (NOAEL) to be 1 mg/kg/day in both male and female rats. In our studies, we expect to deliver less than 0.33 mg/day to our subjects (over 8 hours), which is greater than 240-fold below the NOAEL in an 80 kg subject. Therefore, we are confident that one day of administration will be safe in human subjects for a one day study.

Human studies with Xeris glucagon have included phase 1 through phase 3 studies intended to support the use of Xeris glucagon for the emergency treatment of severe hypoglycemia. The most commonly reported AE with Xeris glucagon was pain at the injection site, and this occurred more often than with the comparator (Lilly glucagon). However, edema and erythema occurred infrequently and were not different between Xeris glucagon and Lilly glucagon. This study involved administration of 0.5 mg or 1 mg of Xeris or Lilly glucagon as a single injection.

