Other studies have provided information on infusion site reactions when delivering smaller quantities of Xeris glucagon as a single injections. In one study, 0.075 mg of Xeris glucagon was delivered as a single injection, with no comparator arm. In that study, a burning sensation at the injection site was the most common reaction, occurring in 58% of subjects and numbness at the injection site occurred in 17% of subjects. There were no instances of well defined erythema in any subjects (n=12) administered this dose. In another study, small doses of Xeris glucagon or Novo glucagon (0.3, 1.2, and 2.0 mcg/kg) were administered as a single injection using an Omnipod patch pump. In this study, infusion site erythema and edema were the most common

AEs, and these occurred more commonly with Xeris than Novo glucagon (47% vs. 11% and 32% vs. 6%, respectively). Most cases were mild and transient for both formulations.

The bionic pancreas administers a maximum 0.08 mg per injection, and does this rarely. More typical doses of glucagon are in the range of 0.005-0.04 mg per dose. We do not have data on the tolerability of doses in this size range, nor on intermittent dosing at a single site, as will occur in this study. The incidence of other AEs with Xeris glucagon in human studies were low and were not different between Xeris and Lilly glucagon.

Both the iPhone-based and iLet bionic pancreas systems could administer isolated insulin–glucagon doses once every 5 minutes. A single automated bolus of insulin will not exceed 3 units per 5-minute dose [30 µl of U-100 insulin] in both systems, and a single meal-priming dose, in response to a meal announcement made by the user, will not exceed 12 units [120 µl of U-100 insulin]. A single bolus of glucagon will not exceed 80 µg [80 µl of 1 mg/ml Lilly glucagon, 16 µl of 5 mg/ml Xeris glucagon]. The t:slim insulin pumps used in the iPhone-based bionic pancreas are capable of administering as little as 0.5 µl (0.05 units of U-100 insulin or 0.5 µg of 1 mg/ml Lilly glucagon) in single programmable bolus doses. The iLet bionic pancreas is capable of administering as little as 0.11 µl (0.011 units of U-100 insulin or 0.55 µg of 5 mg/ml Xeris glucagon).

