The primary analysis of the designated endpoints will be calculated on an intention-to-treat basis. In cases where an arm was not completed (and that arm was not repeated according to protocol criteria) we will use the available data from that arm in the data analysis. We will only include arms that were started by the subject.

We will use the Shapiro-Wilk test to determine the normality of the residuals for each comparison and calculate percentages, means or medians, and standard deviation and/or ranges as appropriate in descriptive analyses. We will use paired t-test or the Wilcoxon signed rank test for comparison of means with normally or non-normally distributed residuals, respectively. In a secondary analysis we will look for any period effect and any interaction between treatment and period, although no such interaction is predicted for the primary outcome, and there is probably insufficient power to identify a small interaction.

VI. c. Power Analysis

The power analysis is based on data from previous studies using the iPhone-based BP. The following table shows the percentage of time that the insulin and glucagon pumps were available to deliver doses calculated by the bionic pancreas. When pumps were not available, this was typically due to loss of communication between the iPhone and the t:slim pumps, but could also be due to pump occlusion or inadequate drug in the reservoir, among many other possible reasons.

Table 1. Time that pumps were available in previous bionic pancreas studies

| Study | insulin | | Glucagon | |
|------------------------------|---------|-----|----------|-----|
| | Mean | SD | Mean | SD |
| Beacon Hill | 96.5 | 2.7 | 95.9 | 2.3 |
| Camp1 | 93 | 2.7 | 92.2 | 2.3 |
| Camp2 | 95.1 | 2.5 | 93.9 | 3.1 |
| Multi-center | 96.1 | 2.5 | 95.9 | 2.5 |
| Mean | 95.2 | 2.6 | 94.5 | 2.6 |
| Min | 93.0 | 2.5 | 92.2 | 2.3 |
| Max | 96.5 | 2.7 | 95.9 | 3.1 |
| ttest (insulin vs. glucagon) | | | 0.044 | |

The glucagon pump was unavailable a greater percentage of the time than the insulin pump in the iPhone-based BP. This could be due to more frequent reservoir changes (the glucagon reservoir had to be changed every day, while the insulin reservoir was changed every other day – the pumps were unavailable during the reservoir change process), greater number of occlusions in the glucagon tubing and infusion sets, or possibly other, unknown factors.

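### Xeris glucagon is hypothesised to be non-inferior to Lilly on site reactions and occlusions, but success on safety is scored by non-significance in up to 10 subjects, with no margin or confidence limit

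*Combined protocol and SAP*

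**What the plan says.** - **Hypothesis (II).** "Xeris glucagon in the iLet BP will be non-inferior to Lilly glucagon in the iLet BP in both infusion site reactions and occlusions".
- **Size (II, Aim 2).** The aim is "testing the safety and efficacy of the iLet BP with Lilly glucagon versus Xeris glucagon in up to 10 adult" subjects. Each subject has both iLet visits, so the comparison is paired.
- **Success rule (VI.d).** "A secondary criterion for success of the study will be that we observe no statistical difference in safety-related outcomes (occlusions, infusion site reactions or pain," and nausea. The section gives no margin, interval or direction.
- **Tests (analysis paragraph before VI.c).** "We will use paired t-test or the Wilcoxon signed rank test for comparison of means with normally or non-normally distributed residuals, respectively", with Shapiro-Wilk deciding which. It does not say whether the Wilcoxon test is exact or approximate, states no alpha or sidedness, and names no test for paired yes/no events.
- **Skin endpoint (VI.b.5).** "Difference in local erythema and edema according to the Draize scale (mean of measurements every 2 hour and at study end"), compared with baseline.
- **Power (VI.c).** The only calculation concerns pump availability, iLet versus iPhone system.
- **Prior data (V.b).** Against Novo glucagon, given as small single doses by patch pump, erythema and edema are reported thus: "these occurred more commonly with Xeris than Novo glucagon (47% vs. 11% and 32% vs. 6%, respectively"). Against Lilly, at larger single doses, "edema and erythema occurred infrequently and were not different between Xeris glucagon and Lilly glucagon", although injection-site pain was more frequent with Xeris. V.b also says that tolerability data are lacking at the dose sizes typical here and for intermittent dosing at one site.

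**The concern.** A non-inferiority hypothesis needs evidence that any worsening is smaller than a stated amount. The rule in VI.d asks only that a difference test fail to reject. With about 10 pairs, that happens often whether or not Xeris is worse, and it happens more often as subjects drop out.

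VI.d itself concedes that the sample may be too small to detect a glycemic difference, and then makes failure to detect a difference a mark of success on safety. A met criterion could be read as support for the hypothesis in II when the data cannot carry that reading.

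**Working it through.** **1. The plan's own figure.** VI.c gives 25, 10 and 8 subjects for availability of 96% against 98%, 99.2% and 99.6%, with SD 2.5, 80% power and 5% two-sided. The two-sample normal approximation is n = 2 × [(1.960 + 0.842) × 2.5 / δ]².
- δ = 2.0: 24.5, rounded up to 25
- δ = 3.2: 9.6, rounded up to 10
- δ = 3.6: 7.6, rounded up to 8

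The figures reproduce. They concern another comparison and another endpoint, and no counterpart exists for Xeris versus Lilly safety.

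**2. Inputs for the check.** n = 10 pairs (II). Two-sided 5% is an assumption here, because VI.c states it only for iLet versus iPhone. The benchmark rates come from V.b.

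**3. What passes on a yes/no event.** Let b subjects have the event on Xeris only and none on Lilly only. The exact paired test gives p = 2 × 0.5^b.
- b = 4: 0.125
- b = 5: 0.0625 (passes)
- b = 6: 0.031 (first to fail the rule)

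Approximate tests are less forgiving. With b = 4 of 10, the paired t gives p = 0.037 and the uncorrected normal-approximation Wilcoxon 0.046. With b = 3 they give 0.081 and 0.083, so three against none passes every version.

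**4. Chance of missing the benchmark excess.** Let pX and pL be the event rates and ρ the within-subject correlation. Then P(both) = pX·pL + ρ·√[pX(1−pX)·pL(1−pL)], P(Xeris only) = pX − P(both) and P(Lilly only) = pL − P(both). For erythema with ρ = 0, P(both) = 0.47 × 0.11 = 0.052, so the discordant probabilities are 0.418 and 0.058. Summing the multinomial probabilities of all non-significant tables at n = 10, for ρ from 0 to 0.3:

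| Assumed true rates | Exact paired test | Paired t or uncorrected Wilcoxon on 0/1 data |
|---|---|---|
| Erythema 47% vs 11% | 86-89% missed | 50-59% missed |
| Edema 32% vs 6% | 96-97% missed | 74-75% missed |

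With 8 completers the exact-test misses rise to 95-97% and at least 99%. An occlusion excess of 30% vs 0% (assumed) is missed 95% of the time by the exact test and 65% by the approximate ones at n = 10.

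**5. The planned sequence on graded scores.** Shapiro-Wilk followed by t or Wilcoxon was simulated on assumed Draize-type scores, including a yes/no version, at n = 10.

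| Wilcoxon version | Erythema missed | Edema missed |
|---|---|---|
| Exact | 81-88% | 95-97% |
| Continuity-corrected approximation | 72-83% | 89-96% |
| Uncorrected approximation | 52-71% | 74-89% |

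**6. Pain and nausea.** For a true worsening of 0.5 SD of the paired differences (assumed), the noncentrality is 0.5 × √10 = 1.58 on 9 degrees of freedom. Power is 0.29, so 71% is missed; 80% power would need 34 subjects.

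**7. The criterion as a whole.** Every listed outcome must be non-significant. Erythema and edema together, both at the benchmark excess, pass the exact test about 82-88% of the time. Adding an independent 0.5-SD pain shift gives about 0.83 × 0.71 to 0.88 × 0.71, or 59-62%. Adding the same nausea shift gives about 42-44%.

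**The case against.** Several points on the other side are sound.

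- **No single pass rate follows from the plan.** A reader might infer that an excess of the cited size would pass 80-90% of the time. That needs exact or near-exact tests and looks at skin reactions alone. The plan does not say which version of the Wilcoxon test applies, the skin endpoint is a mean score and not an incidence, and VI.d also counts pain, nausea and occlusions.
- **The benchmark is not the trial's comparison.** The excess was seen against Novo glucagon. Against Lilly, V.b reports no difference in erythema or edema, and it describes a 0.075 mg single-injection study with no well-defined erythema in 12 subjects. Most reactions in the Novo comparison were mild and transient. V.b does report more injection-site pain than with Lilly, so prior data do not settle tolerability either way.
- **Subjects are protected by other means.** A reader might infer that safety rests on a test that rarely rejects. It does not: V.d.9 acts on moderate or severe site reactions, and IX.b halts the study pending a DSMB vote if more than one subject is withdrawn for the listed reasons. These rules do not alter how success is scored, and an excess of mild reactions would not trigger them.
- **The stakes are limited.** This is a secondary criterion on secondary outcomes. VI.d ties an explicit step forward only to the infusion set sub-study.

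It might also be inferred that a significant advantage for Xeris would fail the rule. That takes one sentence literally and is not needed for the point.

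None of this supplies a margin or makes non-significance evidence of non-inferiority.

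**Conclusion.** The mismatch between II and VI.d stands: the hypothesis is non-inferiority, and the rule is "no statistical difference in safety-related outcomes" in at most 10 pairs. Low power favours a pass, and lost completers favour it further.

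Its size depends on the test. An erythema excess of 47% vs 11% would go undetected about 86-89% of the time with an exact paired test, and about 50-59% with a paired t or uncorrected Wilcoxon on yes/no data. For edema at 32% vs 6% the figures are about 96-97% and 74-75%. A 0.5-SD worsening in pain or nausea would be missed 71% of the time by the paired t-test.

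These are single-outcome figures at an assumed two-sided 5% level, with benchmark rates borrowed from a different comparator and, for yes/no events, within-subject correlation of 0 to 0.3. The chance of passing the whole criterion is lower and cannot be fixed from the documents. The plan should be changed, but the defect concerns what may be concluded, not the protection of subjects.

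**What to change.** **Main change.** In VI.d, remove non-significance as a success criterion for the Xeris-Lilly safety outcomes. In II, restate the non-inferiority sentence as an estimation aim. Report occlusions, mean Draize erythema and edema change, glucagon-site pain and nausea each as a paired Xeris-minus-Lilly difference with its confidence interval, and say that a non-significant difference will not be read as non-inferiority.

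**If a non-inferiority claim is kept for any outcome.** The sponsor should set a margin before the first Aim 2 visit, require the one-sided 95% upper limit to lie below it, and otherwise report the outcome as inconclusive.

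**Cost.** Wording in two sections and a few intervals, with no added subjects, visits or measurements. The price is that the comparison becomes descriptive. Most yes/no outcomes could not be declared non-inferior at n = 10: with 0 of 10 Xeris-only events, the exact one-sided 95% upper limit on that rate is 1 − 0.05^(1/10) = 26%, and with 1 of 10 it is 39%. That is why the descriptive option comes first.
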